**b. External Location[s]:**

- APT Foundation, Inc.  Haskins Laboratories
- Connecticut Mental Health Center  John B. Pierce Laboratory, Inc.
- Veterans Affairs Hospital, West Haven  Other Locations, Specify: CMU

**c. Additional Required Documents (check all that apply):**  N/A

\*YCCI-Scientific and Safety Committee (YCCI-SSC) Approval Date:

\*Pediatric Protocol Review Committee (PPRC) Approval Date:

- \*YCC Protocol Review Committee (YRC-PRC) Approval Date:
- \*Dept. of Veterans Affairs, West Haven VA HSS Approval Date:
- \*Radioactive Drug Research Committee (RDRC) Approval Date:
- YNHH-Radiation Safety Committee (YNHH-RSC) Approval Date:
- Magnetic Resonance Research Center PRC (MRRC-PRC) Approval Date:
- YSM/YNHH Cancer Data Repository (CaDR) Approval Date:
- Dept. of Lab Medicine request for services or specimens form

*\*Approval from these committees is required before final HIC approval is granted. See instructions for documents required for initial submission and approval of the protocol. Allow sufficient time for these requests. Check with the oversight body for their time requirements.*

2. **Probable Duration of Project:** State the expected duration of the project, including all follow-up and data analysis activities. 5 years
3. **Targeted Enrollment:** What is the number of subjects: 86 non-treatment-seeking, alcohol-dependent, family history positive heavy drinkers
  - a. targeted for enrollment at Yale for this protocol? 86 participants  
If this is a multi-site study, what is the total number of subjects targeted across all sites?
  - b. expected to sign the consent form? 172
  - c. expected to complete some or all interventions for this protocol? 86
4. **Research Type/Phase: (Check all that apply)**

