The study will consist of five phases: 1) **Phase 1 (Screening):** We obtain informed consent and evaluate eligibility for the study using clinical assessments and physical exams, if eligible, participants will be scheduled for the rest of the study, 2) **Phase 2 (Baseline):** Participants will complete some memory and mood tasks, participate in the PIT task, and complete a baseline alcohol drinking paradigm (ADP), 3) **Phase 3 (Med 1):** The first 6-8day outpatient medication phase during which participants will come into our clinic every day to take the medication combination they have been assigned and participate in the second ADP on the last day of medication, (participants may be asked to take the medication for up to 13 days, based on scheduling for their overnight stay) Also, in the event that a medication appointment will be missed because the participant is unable to come to the clinic the following day, he/she will be given an extra dose of medication to take home for the next day. The participant will be called the next day as a reminder to take the medication and will also be asked about any adverse events. 5) **Phase 4 (Washout):** At least 6-8 day washout phase (length of washout based on hospital scheduling) and 6) **Phase 5 (Med 2):** Participants will be randomized to receive another medication combination for 6-8 days which will culminate in the third ADP (again, this is based on scheduling for the overnight at the hospital and can be extended to 13 days). In the event that a participant is unable to make it to one of the overnight visits, and needs to discontinue one of the medication periods early due to personal circumstances, we would like to have the option of restarting the medication. We do not believe that this will increase risk to participants since they would have already taken the medications during an earlier phase. It is essential that participants complete all parts of the study for us to be able to use the data to evaluate the effects of combining naltrexone and memantine on drinking behaviors.

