Once all phases are complete, participants will be scheduled for a 1-week follow up appointment. We will record any remaining adverse events and assess drinking behavior. A clinical psychologist will talk to all participants about their drinking behavior and if they are interested will provide them with treatment referrals. The one-week and one-month follow-up sessions will be conducted with all participants, even those who drop out during the course of the study.

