i) Psychophysiological Measures: These will include heart rate and blood pressure monitored using a Critikon Dinamap while skin temperature will be measured using Yellow Springs Instruments 4600 precision thermometer. The cuff of the Dinamap will be on the subject's dominant arm while the probe of will be attached to the middle finger of the subject's non-dominant arm. These data will be further used to examine the safety of using the medication combination during alcohol self-administration.

4. **Statistical Considerations:** Describe the statistical analyses that support the study design.

All outcomes will be summarized descriptively and assessed for normality prior to analysis using normal probability plots and Kolmogorov test statistics. Transformations or nonparametric analyses will be performed as necessary. In the mixed models described below, the correlation between repeated measures on an individual will be modeled using random effects and/or structured variance-covariance matrices. The best-fitting variance-covariance structure will be determined by information criterion. The mixed-effects approach is advantageous in that it is unaffected by randomly missing data and allows greater flexibility in modeling the correlation structure of repeated-measures data (Gueorguieva and Krystal, 2004). In the models below, we will test for order effects, although any such effects should be greatly minimized with the inclusion of the baseline session. All tests will be two-sided and considered statistically significant at alpha=.05. Significance levels for secondary comparisons will be adjusted for multiple tests using the Bonferroni correction, basing the adjustment on the number of conceptually related statistical tests within each hypothesis.

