### ***Power Analysis***

This is a pilot trial and we will use the data to determine initial tolerability and effect size estimates for future trials. We will recruit a total of 30 completers in this trial, 10 in each group.

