**1a. Assessment of Current Health Provider Relationship for HIPAA Consideration:**

Does the Investigator or any member of the research team have a direct existing clinical relationship with any potential subject?

- Yes, all subjects
- Yes, some of the subjects
- No

If yes, describe the nature of this relationship.

**2. Subject Population** Provide a detailed description of the targeted involvement of human subjects for this research project.

86 healthy heavy drinkers who are not currently seeking treatment for their drinking behavior, between 21-55 years of age.

3. **Inclusion/Exclusion Criteria:** What are the criteria used to determine subject inclusion or exclusion? How will eligibility be determined, and by whom?

Inclusion criteria:

- 1) Ages 21-55
- 2) Able to read English at 6th grade level or higher and to complete study evaluations
- 3) Meet DSM-IV criteria for alcohol dependence or abuse (assessed using the SCID)
- 4) Family history criteria (assessed using the FHAM; see Assessment section)  
Family history positive subjects: At least one first-degree relative with alcoholism as determined by the FHAM  
Family history negative subjects: No first degree relative with alcoholism and no 2nd degree relative with alcoholism unless the participant cannot answer details about the 2nd degree family member's drinking consequences on the FHAM.  
(Average weekly alcohol consumption of standard drinks of at least 25-70 drinks for men and 20-65 drinks for women)
- 5) No more than 3 days abstinence/week in order to maximize the likelihood that subjects will choose to drink during the laboratory sessions

Exclusion criteria:

- 1) Individuals who are seeking alcohol treatment or have been in alcohol treatment within the past 6 months
- 2) Current DSM-IV dependence criteria for other substances, other than nicotine
- 3) Positive test results at more than one baseline appointment on urine drug screens conducted for opiates, cocaine, benzodiazepines, and barbiturates
- 4) Regular use of psychoactive drugs including anxiolytics and antidepressants
- 5) Psychotic or otherwise severely psychiatrically disabled; scores above 2 SD of the mean on the Wisconsin Psychosis Proneness scale
- 6) Medical conditions that would contraindicate the consumption of alcohol
- 7) Medical conditions that would contraindicate the use of naltrexone such as hepatic dysfunction

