#### **SECTION IX: PROTECTION OF RESEARCH SUBJECTS**

1. **Risks:** Describe the reasonably foreseeable risks, including risks to subject privacy, discomforts, or inconveniences associated with subjects participating in the research.

The major potential risks in this study are related to administration of alcohol, memantine, N-acetyl cysteine, naltrexone, and the blood draw during the physical exam and alcohol drinking period.

1) Memantine:

An NMDA antagonist, has been approved by the FDA for the treatment of moderate to severe Alzheimer's disease in the US. Numerous studies have found memantine to be safe and associated with few side effects. In a study of 252 patients, 17% of memantine-treated patients and 10% of placebo-treated patients discontinued treatment because of adverse events during 28-weeks of treatment. The most common side effects occurring with equal frequency in memantine and placebo groups included agitation, urinary incontinence, urinary tract infections, insomnia and diarrhea. Side effects occurring at a higher rate in memantine-treated patients included dizziness (7%), headache (6%), constipation (6%), confusion (6%), insomnia (less than 1%) and hallucinations (less than 1%). Since memantine could also cause drowsiness or dizziness, participants will be told to use caution when driving, operating machinery or performing other hazardous activity. Memantine is in FDA category B which means that it is not expected to be harmful to an unborn baby but since there has been minimal use of this agent in a young patient population (such as the one in this proposal) we have chosen to be cautious and exclude women who are pregnant or nursing. Such individuals could not be included in the current proposal anyway since we are administering alcohol to all subjects. The major route of memantine elimination is renal and therefore the use of this drug in patients with renal impairment is not recommended. There is also some question about its use in those with seizure disorders of liver disease. Since liver disease is often seen in alcohol-dependent subjects we are proposing to exclude individuals with kidney disease, liver disease or seizure disorder.

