Because this study may not have direct benefits to the individual participant, subjects will be offered payment for their participation. Subjects will have the opportunity to receive up to \$2103 for completing all phases of the study. Payment for the screening interview will be \$50, and they will receive an additional \$50 for the physical examination; we have found that payments for these appointments encourages attendance as scheduled. Subjects will also receive \$50 for the PIT task, \$150 for participating in the first ADP, up to \$160 for taking medication during Med 1 (6-8 days, up to 13 days if necessary), \$200 for participating in the second ADP, \$40 for complying with the 6-8 day washout procedures, up to \$160 for taking medication during Med 2 (6-8 days, up to 13 days if necessary), \$250 for participating in the third alcohol-drinking paradigm, and a bonus of \$200 for completing all 3 drinking paradigms given the within-subjects design. Subjects will earn an additional \$10 per day for transportation during phases 2, 3 and 5. Subjects will also receive an additional \$10 for keeping each scheduled appointment, once they are enrolled (after the physical exam) for a total of \$190. Subjects will also have the opportunity to earn an extra \$36 during each of the self- administration periods as well as \$75 for computer tasks done at the outpatient and inpatients appointments. Lastly, they will earn \$30 for completing each of the two follow-up appointments. This progressively increasing payment structure was developed in order to motivate subjects to complete all phases of the study, since obtaining complete data in this within-subjects crossover study is the key to achieving the goals of the project. We are trying to avoid early drop out by using increasing incentives for completion of the entire study. Subjects will be reimbursed \$20 for valet parking at Yale New Haven Hospital for overnight stays during the ADP's. They will also be compensated \$25 if they are asked to come back for any repeat lab work (blood or EKG). If a participant comes in to be consented and decides, after learning more about the study, he/she is not interested in participating, we will discontinue the intake appointment and compensate you \$10 for his/her time.

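### Does the lack of a named analysis set turn the efficacy and tolerability analyses into completers-only analyses?

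*Combined protocol and SAP*

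**What the plan says.** Four parts of the combined protocol and SAP bear on who is analysed.

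- **Section V, Power Analysis.** The study is called a pilot meant to yield tolerability and effect-size estimates. The target is "We will recruit a total of 30 completers in this trial, 10 in each group". No power, SD or dropout rate is given.
- **Section V, item 3 (Research Plan).** After the option of restarting an interrupted medication period, the text adds: "It is essential that participants complete all parts of the study for us to be able to use the data". The sentence goes on to limit this to evaluating the naltrexone and memantine combination on drinking behaviour.
- **Section V, item 4 (Statistical Considerations).** "The mixed-effects approach is advantageous in that it is unaffected by randomly missing data". Aim 1 then specifies a linear mixed model for total drinks, with treatment as a within-subjects factor. Neither this section nor the aims define an analysis population.
- **Section X, item 2 (Payments).** The rising payment schedule is justified because "obtaining complete data in this within-subjects crossover study is the key to achieving the goals of the project".

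The headcounts differ. The Targeted Enrollment item reads "expected to complete some or all interventions for this protocol? 86", and Section VII describes "86 healthy heavy drinkers who are not currently seeking treatment for their drinking behavior". Dropouts are expected and followed: "The one-week and one-month follow-up sessions will be conducted with all participants, even those who drop out during the course of the study".

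**The concern.** Three statements lean towards completers and one leans towards all available data, and no sentence settles the matter. An analyst who took the research-plan remark literally would discard on-medication drinking sessions from people who finished the second alcohol-drinking session (ADP 2) but not the third (ADP 3). One who followed the mixed-model rationale would keep them. If the set were chosen after the data had been seen, that choice could influence the result.

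The worry is sharper for tolerability, because a completers-only set contains, by construction, nobody who stopped for side effects. The Risks section reports a study in which "17% of memantine-treated patients and 10% of placebo-treated patients discontinued treatment because of adverse events", so completion can depend on treatment. Those figures come from 28 weeks of treatment in another setting and say nothing about the rate expected here. The gap between 86 and 30 also makes the amount of partial data look large.

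**Working it through.** **1. The plan's own figures.** Three add-on conditions (memantine, NAC, placebo) × 10 = 30, which agrees with the stated total. The largest possible number of non-completers is 86 − 30 = 56, or 56/86 = 65.1%. To have 56 people with a usable on-medication session, all 86 would have to start medication, 65% would have to fail to complete, and every one of those would have to reach ADP 2. Section IX, item 2 (Alcohol Challenges) allows people who take no choice drinks at the first drinking session to be discontinued before any medication, and they would have no such session. So 56 is a ceiling. For scale, 30 completers need 30/(1 − d) enrolled, rounded up: 34 at d = 10%, 43 at 30%, 60 at 50%.

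**2. What each statement governs.** The Power Analysis sentence sets a recruitment target. The Payments sentence explains incentives. The research-plan sentence supports the restart option and concerns drinking outcomes. Only Statistical Considerations addresses how incomplete data are analysed. The Aim 1 outcome is a single total per session, so for that aim a randomly missing observation is a missing session. The stated advantage has content there only if people with a missing session stay in the model.

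**3. Tolerability.** The Research Plan has adverse events recorded daily. The Study Medication section has tolerability monitored at the daily clinic visits. Section IX, item 3 monitors adverse events for each participating subject. The Exploratory Aims analyse events seen on combination treatment, with no completion condition. The one-week follow-up, which dropouts also attend, records remaining events. Nothing ties this analysis to completion.

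**4. Precision (illustration).** Assumptions: random-intercept model with period and two treatment contrasts; 30 completers in three treatment pairs of 10; K further people with ADP 2 only, spread evenly over conditions; SD of the paired difference set to 1; within-person correlation 0.3 or 0.9. Half-width = SE × t(27) = SE × 2.052.

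| K | SE (0.3 / 0.9) | Half-width (0.3 / 0.9) | Reduction from K = 0 |
|---|---|---|---|
| 0 | 0.2377 / 0.2560 | 0.488 / 0.525 | – |
| 14 | 0.2191 / 0.2523 | 0.450 / 0.518 | 8% / 1% |
| 28 | 0.2027 / 0.2484 | 0.416 / 0.510 | 15% / 3% |
| 56 | 0.1807 / 0.2417 | 0.371 / 0.496 | 24% / 6% |

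Using only within-person information from the 30 completers gives 0.2582 × 2.052 = 0.530. Letting the degrees of freedom rise with K shortens the intervals slightly further (0.359 / 0.481 at K = 56).

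**5. Selection (illustration).** Same model, true effect zero. Dropout after ADP 2 depends on ADP 2 drinking only on a combination, with an odds ratio of 2 per SD. Absolute completers-only bias, in SD of the paired difference:

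| Completing | Bias at correlation 0.3 / 0.9 |
|---|---|
| 87% | 0.03 / 0.01 |
| 72% | 0.06 / 0.03 |
| 50% | 0.11 / 0.05 |
| 36% | 0.13 / 0.06 |

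The mixed model on everyone with an on-medication session stays within 0.003 of zero. If dropout depends on ADP 2 drinking alike in all conditions, both analyses give about zero. At 72% completing, the worst bias is 0.06/0.488, about one eighth of the half-width.

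**The case for a change.** The best case for a change is that the silence is real and the research-plan remark is the document's only explicit statement on when data can be used. A mixed model fitted to completers is still a mixed model, so naming the method does not name the population. The plan also keeps two-sided tests at 0.05 and intends its estimates to feed later trials. Writing the set down would cost a sentence or two and would close off a choice made after seeing the data.

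Part of this stands. The efficacy set is not named, and the remark sits awkwardly beside the mixed-model rationale. It is also unclear how 86 relates to 30, and what a group is when three conditions are given over two periods. If it means a pair of treatments, 10 of the 30 completers never receive naltrexone alone. That is a separate question of design description.

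The rest is weaker. The completers-only reading is inferred from statements about recruitment, payment and restarting, and the tolerability harm needs a restriction that the plan does not contain. Naming everyone with at least one on-medication drinking session as the efficacy set would mostly record the method's default. It would still leave out anyone who stopped during the first medication period before ADP 2, which is where early intolerance would show.

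**Conclusion.** No change is called for. The plan omits a definition that it could have given, but the analysis it specifies has an ordinary meaning: fit the mixed model to all on-medication sessions, and describe adverse events in those who took the medication. The statements that seem to say otherwise serve other purposes.

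Any loss from the narrower reading depends on values the documents do not supply. At a correlation of 0.9, adding 14 to 56 one-session participants shortens the interval by 1% to 6%. At 0.3 it shortens it by 8% to 24%, the upper figure at the ceiling of 56. Completers-only bias is 0.01 to 0.06 SD with 72% to 87% completing, against a half-width near 0.5. It reaches 0.13 only with 36% completing, a correlation of 0.3, and outcome-dependent dropout confined to the combinations. A rule stated elsewhere that restricted the efficacy or adverse-event analysis to completers would change this conclusion. The documents contain none.

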## **SECTION VI: RESEARCH INVOLVING DRUGS, DEVICES, BIOLOGICS & PLACEBOS**

1. **Identification of Drug, Device or Biologic:** What is (are) the **name(s)** of the drug(s), device(s) or biologic(s) being used? Identify whether FDA approval has been granted and for what indication(s).

Memantine, or 1-amino-3, 5-dimethyladamantane hydrochloride, is a moderate affinity noncompetitive NMDA antagonist with voltage-dependent binding characteristics. FDA approved as a pharmacotherapy for the treatment of moderate to severe Alzheimer's disease.

Naltrexone is an FDA approved drug that is used in the treatment of alcoholism and opioid addiction.

N-acetyl cysteine is FDA approved for use as a mucolytic agent for bronchopulmonary disorders (e.g. Grandjean et al., 2000) and as an oral or intravenous antidote to treat acetaminophen poisoning (Smilkstein et al., 1988). NAC is a precursor of glutathione synthesis and is available worldwide in intravenous, oral and nebulizer forms and is also sold over the counter in health food stores.

All protocols which utilize a drug, device or biologic **not** approved by, but regulated by, the FDA must provide the following information:  **Not applicable to this research project**

The new agent being used in this protocol, NAC, is freely available over the counter in health food stores and has been used off-label safely for a wide number of indications at the doses proposed. Therefore, we do not feel we would need an IND for this protocol.

- i. What is the Investigational New Drug (IND) or Investigational Device Exemption (IDE) **number** assigned by the FDA?
- ii. For IDE's: Did the FDA approve this IDE as a Category A (experimental/investigational) or as a Category B (non-experimental/investigational)?
- iii. Who holds the IND or IDE?

The clinical investigation of a drug product that is lawfully marketed in the United States may be exempt from the requirements for filing an IND. If there is no IND and an exemption is being sought, complete the following: Exempt

- i. Is the intention of the investigation to report to the FDA as a well-controlled study in support of a new indication for use or to be used to support any other significant change in the labeling for the drug?  Yes  No
- ii. If the drug that is undergoing investigation is lawfully marketed as a prescription drug product, is the intention of the investigation to support a significant change in the advertising for the product?  Yes  No
- iii. Does the investigation involve a route of administration or dosage level or use in populations or other factor that significantly increases the risks (or decreases the acceptability of the risks) associated with the use of the drug product?  Yes  No
- iv. Will the investigation be conducted in compliance with the requirements for institutional (HIC) review and with the requirements for informed consent of the FDA regulations (21 CFR Part 50 and 21 CFR Part 56)?  Yes  No
- v. Will the investigation be conducted in compliance with the requirements regarding promotion and charging for investigational drugs?  Yes  No

2. **Background Information:** Provide a description of previous human use, known risks, and data addressing dosage(s), interval(s), route(s) of administration, and any other factors that might influence risks. If this is the first time this drug is being administered to humans, include relevant data on animal models.

Memantine has been used in the treatment of patients with Parkinson's disease [48], dementia [49-51] and neurogenic bladder dysfunction in spasticity [52]. The drug was also found to be stimulating or vigilance-enhancing in comatose patients [53]. Memantine induces open-channel blockade of NMDA receptors and has been observed to be partially trapped in NMDA receptor channels. There have been a number of studies of memantine in healthy volunteers. Memantine has been shown to increase intracortical inhibition and reduce intracortical facilitation [54] and found to have no significant effects on mood, attention or immediate and delayed verbal and visuospatial memory [55]. Memantine has vigilance-enhancing effects in healthy elderly volunteers [56] but no effects on a series of perceptual and psychomotor tasks, including temporal discrimination, reaction time, critical flicker fusion frequency and signal detection [57]. Memantine is completely absorbed from the GI tract and maximum plasma concentrations occur between 3-8 hours after oral administration. It is 100% bioavailable after oral administration and has been shown to have a linear pharmacokinetic profile that is not influenced by age, sex or food (Forest Labs, data on file). Approximately 80% of the agent circulates as unchanged parent drug, the mean terminal elimination half-life is 60-100 hours and it is eliminated renally [43]. Memantine was well tolerated in randomized double-blind, placebo-controlled trials for patients with moderately severe to severe dementia, moderate to severe Alzheimer's disease as well as vascular dementia [43, 58, 59]. The most common adverse events observed in clinical trials are diarrhea, insomnia, dizziness, headache, constipation, and confusion [60]. In patients with severe renal impairment or hepatic problems the use of memantine has not been systematically evaluated and is not recommended.

Naltrexone, an opioid antagonist, is widely used in the treatment of opioid addiction and more recently has been found to be beneficial in the treatment of alcoholism. Numerous studies have found naltrexone use to be safe and rarely associated with toxicity or severe side effects. The most frequent reported side effects are gastrointestinal in nature. Those include epigastric pain,

nausea and vomiting. Other, less frequent side effects include nervousness, dizziness, headaches, blurred vision, low energy, fatigue, sleepiness, joint and muscle pain and insomnia. Hepatotoxicity, the most serious potential side effect, has been shown in studies using very high doses of naltrexone (1400 to 2100 mg per week). At the doses used in this study naltrexone has not been reported to produce hepatotoxic effects. However, we will monitor liver function tests prior to the study and exclude individuals with evidence of significant hepatocellular injury (AST, ALT  $>3$ x normal established in pregnant and nursing women, they will be excluded from participation. Naltrexone can also precipitate or exacerbate opiate withdrawal, as a result subjects with abuse or dependence on opiates will be excluded from the study on the basis of self-report and urine drug screens.

Since naltrexone is an opiate antagonist, alternative nonopioid methods of analgesia can be used. In an emergency situation requiring opioids, the amount of opioids necessary for analgesia may be greater than usual, and the resulting respiratory depression may be deeper and more prolonged. As a result, a rapidly acting analgesic which minimizes respiratory depression is preferred and the amount of the analgesic administration titrated to the needs of the patient in a setting equipped and staffed for cardiopulmonary resuscitation. As a result, subjects will be given a card showing that they may be receiving naltrexone. This card will provide detailed information to medical personnel describing the special precautions necessary in the event that the subject should require pain management. In addition, this card will have a code number on it that can be used to identify which medication the subject is on. A phone number of the pharmacy and for the physician on call at the Connecticut Mental Health Center will be listed on the card in the event of an emergency in which it is necessary to determine whether the subject is on active naltrexone.

NAC (also known as Acetylcysteine) has been safely used for several decades in adults and children as a long-term treatment for chronic bronchitis. It has been found to be cost-effective to use and generally well tolerated with mild, most commonly gastrointestinal adverse effects. This dose of NAC (2400 mg) was observed to be safe and tolerable in cocaine dependent participants (e.g. Larowe et al., 2006).

